### 8.3.2. Sensitivity Analyses for Primary Endpoint

Several sensitivity analyses will be performed for the primary endpoint.

- By considering all deaths (and not just deaths due to disease progression) as non-responders. This will be performed using the mITT population.
- Using multiple imputations under assumptions of Missing at Random (MAR) as described below
- Using the ITT population instead of the mITT populations based on (MAR) as described below
- Using multiple imputations under assumptions of Missing Not at Random (MNAR) as described below
- Identical to the primary endpoint, but using the EE population instead of the mITT population
- In addition, sensitivity analyses may be added including/excluding data collected that may have been impacted due to COVID-19.

The method of multiple imputations creates multiple data sets where unobserved data are imputed prior to fitting the linear regression. In both sensitivity analyses, the method of multiple imputations (MI) using Pattern Mixture Model will be used.

In the first sensitivity analysis, an assumption of Missing at Random (MAR) will be made and subject's missing data will be imputed using those with available data within the treatment group they were assigned to. In the second sensitivity analysis, an assumption of Missing Not at Random (MNAR) will be made based upon an approach similar to above using multiple imputations with missing data for subjects imputed using the available data for Placebo participants.

The method of multiple imputation uses SAS PROC MI and MIANALYZE to generate multiple complete datasets and combine the model results from them. To ensure robustness of results 100 complete datasets will be generated with the initial seed value set at 123.

### 8.4. Analysis of key Secondary Efficacy Endpoints

All analyses of the key secondary efficacy endpoints will be performed using the mITT population.

The first key secondary efficacy endpoint is to evaluate the efficacy of NurOwn® (MSC-NTF cells) vs. placebo as measured by the proportion of participants whose disease progression is halted or improved as measured by a 100% or greater improvement in post-treatment slope vs. pre-treatment slope in ALSFRS-R score at 28 weeks following the first treatment. Note, an improvement of 100% or greater means halt or improvement in disease progression (post-treatment slope) as measured by the ALSFRS-R. As in the analysis of the primary endpoint, all deaths due to disease progression will be considered as non-responders. If pre-treatment slope is 0, the % change in post-treatment slope compared to pre-treatment slope will be considered missing. The impact of this will be explored through a sensitivity analysis defined below.

Each subject's pre- and post-transplantation slope, change and percent change in slope will be calculated and listed for each post baseline timepoint.

Percentage change in slope through Week x =  $100 * ([\text{post-transplantation slope through Week x} - \text{pre-transplantation slope from screening through baseline}] / \text{Absolute Value} [\text{pre-transplantation slope from screening through baseline}])$ . Note, the absolute value is taken in the denominator since the pre-transplantation slope is often negative.

The hypothesis testing for the first secondary endpoint of percentage change in slope at 28 weeks following first treatment will follow the same methodology as the primary endpoint described above.

Since percentage change in post-treatment slope as compared to pre-treatment slope is considered missing when the pre-treatment slope is 0, and can be very large for very small values of pre-treatment slope, a sensitive analysis will be performed considering all subjects with post-treatment slope  $\geq 0$  as responders and all deaths due to disease progression as non-responders.

The next key secondary efficacy endpoint is to evaluate the efficacy of NurOwn® (MSC-NTF cells) vs. placebo as measured by change in the ALSFRS-R score between baseline and 28 weeks following the first treatment. The null hypothesis of no difference between treatment groups will be tested using a mixed effect repeated measures (MMRM) model with the change in ALSFRS-R score from baseline as the dependent variable and treatment group, visit, baseline ALSFRS-R score, duration from onset of symptoms to first treatment, site of onset (Limb vs Limb & Bulbar), Riluzole use and ALSFRS-R slope pre-treatment as main effect and the interaction between treatment group and visit.

An unstructured covariance-structure will be used to model within-subject errors. If this fails to converge the covariance-structures below will be used in the order specified. The Kenward-Roger approximation will be used to estimate denominator degrees of freedom for unbalanced data. Repeated statement was used because the random variable involves repeated measurement at different visits. Significance tests will be based on LS Means.

If the unstructured covariance structure fails to converge following covariance structures will be tested in order below. The first covariance structure that converges will be used.

1. Toeplitz with heterogeneity (TOEPH)
2. Autoregressive with heterogeneity (ARH (1))
3. Compound symmetry with heterogeneous variances (CSH)
4. Toeplitz (TOEP)
5. Autoregressive (AR (1))
6. Compound symmetry without heterogeneous variances (CS)

For analysis of ALSFRS-R subscales of Bulbar function (0-12 points), Respiratory function (0-12 points), Gross motor function (0-12 points), Fine motor function (0-12 points) and Gross & Fine motor function combined (0-24) a responder analysis similar to the primary endpoint and a MMRM analysis as described above will be performed.

[REDACTED]

The next key secondary efficacy endpoint to be tested will be the combined analysis of function and survival (CAFS)

Each subject's CAFS score is used as the dependent variable for analysis using an ANCOVA model with treatment as a fixed effect and adjusted for covariates baseline ALSFRS-R score, duration from onset of symptoms to first treatment, site of onset (Limb vs Limb & Bulbar), Riluzole use and ALSFRS-R slope pre-treatment. The generalized Gehan-Wilcoxon rank test will be performed as a supportive analysis.

SVC measures the maximum amount of air a patient can exhale in a single breath. SVC is reported as a percent of normal for gender, height, and age. Three measures of SVC are captured at each visit and the percent of normal for gender, height, and age is recorded for the highest of the three SVC measures. If the variability of the raw score is 10% or greater during the first 3 trials, up to 5 trials can be done. The percent of normal for gender, height, and age using the average measure at a given visit will be used for summaries.

At each visit the average of the valid assessment will be used.

The next key secondary efficacy endpoint to be tested will be the change from baseline to Week 28 in SVC using MMRM. The MMRM model used will be the same as the one indicated above for ALSFRS-R, with baseline ALSFRS-R and pre-treatment ALSFRS-R slope replaced by baseline SVC and pre-treatment SVC slope.

The next key secondary efficacy endpoint to be tested sequentially will include comparison between treatment groups the time from baseline to the subject having a tracheostomy or dying (also referred to as tracheostomy-free survival) as described below.

The Kaplan-Meier method will be used to estimate the proportion of subjects with tracheostomy-free survival along with the median and interquartile range for tracheostomy-free survival. A Kaplan-Meier plot of the time to tracheostomy-free survival will also be provided.

For comparison of tracheostomy-free survival between treatment groups, a log rank test will be used. In addition, a Cox proportional hazards model will be used to estimate the hazard ratio and 95% confidence intervals for tracheostomy-free survival between treatment groups. The model will include treatment, baseline ALSFRS-R score, duration from onset of symptoms to first treatment, site of onset (Limb vs Limb & Bulbar), Riluzole use and ALSFRS-R slope pre-treatment as fixed factors.

The next key secondary efficacy endpoint tested will be a comparison between treatment groups for the time to death due to disease progression using the same methodology as above. As a sensitivity analysis time to death due to any cause will also be analyzed.

Additional subgroups of interest based on clinical assessment prior to first treatment, duration from onset of symptoms to first treatment, pre-treatment slope, biomarkers or genetic testing, etc. may also be performed if there is an imbalance between treatment groups of subjects within each subgroup and there are a sufficient number of subjects within the subgroups.

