1.4.1. Inclusion Criteria

Study participants meeting all of the following criteria will be allowed to enroll in the study:

1. Males and females ages 18 to 60 years old, inclusive, at the Screening Visit.
2. ALS diagnosed as possible, laboratory-supported probable, probable, or definite as defined by revised El Escorial criteria.
3. Having onset of ALS disease symptoms, including limb weakness within 24 months at the Screening Visit.
4. ALSFRS-R ≥ 25 at the screening visit.
5. Upright Slow Vital Capacity (SVC) measure $\geq 65\%$ of predicted for gender, height, and age at the Screening Visit (See [Appendix 3](#)).
6. Decline in ALSFRS-R total score of 3 or more points in the 12 weeks preceding randomization.
7. Participants must be taking a stable dose of riluzole, or no riluzole at all (riluzole-naïve participants are permitted in the study), for at least 30 days prior to the Screening Visit and be willing to maintain the riluzole dose for the duration of the study.
8. Women of childbearing potential shall either be surgically sterile, or must agree not to become pregnant for the duration of the study. Women must be willing to undergo a serum pregnancy test at screening, one week before bone marrow aspiration, at the visit prior to each MSC-NTF transplantation and at the conclusion of the study. Participants

of childbearing potential must agree to use a medically approved form of birth control (abstinence, intrauterine device (IUD), oral contraception, barrier and spermicide or hormonal implant) throughout the duration of the study and for at least 3 months following the last transplantation. For those women who are sexually active and using oral contraceptives, a second form of barrier contraception is required. Men must be willing to consistently use two forms of contraceptive if their partners are of childbearing age.

9. Capable of providing informed consent and willing and able to follow study procedures, including willingness to undergo multiple/repeated lumbar puncture.
10. Geographic accessibility to the study site and willingness and ability to comply with follow-up.
11. Citizen or permanent resident of the US or Canadian citizen able to travel to a US site for all follow-up study visits

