## 2. INTRODUCTION

Amyotrophic lateral sclerosis (ALS) is a fatal, progressive, neurodegenerative disease characterized by motor neuron cell death in the brain and spinal cord, accompanied by rapid loss of muscle control and eventual complete paralysis. There is currently no available treatment to prevent its progressive course, and life expectancy of patients is usually 3 to 5 years after diagnosis.

The purpose of the BCT-002 Phase 3 study is to evaluate the efficacy and safety of three repeated administrations of NurOwn® (MSC-NTF cells) as compared to placebo delivered intrathecally every two months to participants with ALS (ALSFRS-R  $\geq$  25 at the Screening Visit).

The primary and key secondary efficacy endpoints will be assessed based upon improvement in ALSFRS-R scores. Blood and CSF samples will be collected for biomarker analyses and DNA will be collected to identify specific ALS mutations and ALS related genes that may reveal important prognostic variables in post hoc analyses.

The current study is a 1:1 randomized, double-blind, placebo-controlled multicenter study. The control group will be administered placebo (excipient). It is expected that approximately 100 participants in each the NurOwn® (MSC NTF cells) and placebo arms will provide an adequate number of participants in order to demonstrate a higher proportion of participants in the MSC-NTF group responding to treatment compared to Placebo.

The purpose of this statistical analysis plan (SAP) is to describe the planned analyses and data displays to be included in the Clinical Study Report (CSR) for Protocol BCT-002-US.

This SAP was developed in accordance with the ICH E9 guideline and current best practices for statistical analyses of Phase III clinical trials.

The first draft of the SAP was submitted to the FDA in November 2017 prior to the first subject being dosed. This final version incorporates feedback received from the FDA and additional details related to the analyses.

Any additional changes to the SAP such as finalizing the EE populations, additional analyses planned, etc. will be made prior to database lock and unblinding of the study data and captured in an appendix to the SAP.

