#### 4.3. Sample Size Considerations

Since the primary efficacy endpoint is based upon the percentage of responders who demonstrate a  $\geq 1.25$  points/month improvement in ALSFRS-R post treatment slope as compared to their pre-treatment slope, the sample size for this study is based upon estimation of the percentage of participants on NurOwn®, excluding slow progressors, who were responders at 12 weeks as observed in the previous Phase 2 BCT-001 US study.

At 12 weeks post-treatment 53% of NurOwn® (MSC-NTF cells) treated participants, excluding slow progressors, were observed to have an improvement in post-treatment slope using either the thresholds of  $\geq 1.0$  Points / month or  $\geq 1.5$  points / month.

The best estimate of the percentage of placebo participants who will be responders is based upon the % of responders among those receiving placebo at 24 weeks. At 24 weeks post-treatment, 17% of placebo participants were responders using the threshold of  $\geq 1.0$  Points / month and 0% using the threshold of  $\geq 1.5$  points / month.

Accounting for the longer duration of this study, missing data due to discontinuations and potentially fewer responders in the NurOwn® treated group we estimate the true percentage of responders who improve  $\geq 1.25$  point/month on NurOwn® to be 35% and on Placebo to be 15%. Utilizing a Chi-square test with Type I error rate of 0.05 two-sided and 90% power we would require 97 participants per treatment arm.

The true % of responders using the criteria of  $\geq 100\%$  improvement is also expected to be around 35% treated and 15 % placebo.

A sample size of approximately 100 participants per arm (approximately 200 participants total) will be randomized.

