## 8.2. Multiple Comparisons and Multiplicity

The primary efficacy endpoint and key secondary efficacy endpoints will be tested sequentially to account for multiplicity and preserve overall Type I error. No adjustments will be made for multiple comparisons in testing other secondary or exploratory efficacy endpoints.

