## 8.3. Analysis of the Primary Efficacy Endpoint

### 8.3.1. Primary Efficacy Analysis

The primary efficacy endpoint is based upon the ALSFRS-R which is a validated scale based upon 12 items, each rated from 0 to 4. Scores of 4 are Normal and 0 are the worst. Note the ALSFRS-R total score is between 0 and 48. The slope is determined by fitting a linear regression using all assessments between the time points mentioned.

A subject is defined as a responder if his/her rate of disease progression as measured by the ALSFRS-R slope (rate of decline per month fit using linear regression) over 28 weeks from baseline improves by  $\geq 1.25$  points/month as compared to the disease progression over the pre-treatment period. All deaths related to disease progression will be defined as non-responders.

The pre-transplantation slope in ALSFRS-R score per month is calculated using all available ALSFRS-R scores from the screening visit through the last pre-transplantation visit (including the assessment pre-transplantation at the baseline first transplantation visit). The post-transplantation slope through any post-transplantation visit is calculated from the baseline visit (last available ALSFRS-R prior to and inclusive of the transplantation visit) through each post-transplantation visit (using all available ALSFRS-R scores post baseline).

The above slopes are computed by fitting a linear regression on ALSFRS-R scores as the dependent variable and days as the independent variable. The slope from the linear regression is a change in ALSFRS-R score per day. This is converted to a change in ALSFRS-R score slope per month by multiplying the slope by 30.4375 [365.25/12] to obtain a slope per month (Change in ALSFRS-R score per month).

The null and alternative hypothesis are as follows:

$$H_0: P_t = P_p$$

$$H_a: P_t \neq P_p$$

Where  $H_0$  and  $H_a$  are the null and alternative hypothesis respectively and  $P_t$  and  $P_p$  are the proportion of participants in the treated group and placebo group whose post-treatment slope over 28 weeks from baseline as compared to the pre-treatment slope in the overall ALSFRS-R score improves by  $\geq 1.25$  points/month.

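### The ALSFRS-R MMRM gives pre-treatment slope one coefficient for all visits; under unstructured covariance it adds almost no precision at Week 28, and a slope-by-visit term would avoid an SE about 1–6% larger

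*SAP*

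**What the plan says.** The second key secondary endpoint is change in ALSFRS-R from baseline to Week 28. SAP 8.4 analyses it by MMRM with "change in ALSFRS-R score from baseline as the dependent variable". The main effects are treatment, visit, baseline score, symptom duration, site of onset, riluzole use and prior slope. The list ends with "ALSFRS-R slope pre-treatment as main effect and the interaction between treatment group and visit", so treatment by visit is the only interaction in the visible text.

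On the covariance: "An unstructured covariance-structure will be used to model within-subject errors". Six simpler structures follow, to be used only if it does not converge.

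SAP 8.3.1 computes the prior slope by a regression for each subject over all pre-transplant scores, "including the assessment pre-transplantation at the baseline first transplantation visit". The baseline score therefore enters the covariate and is also subtracted in the outcome.

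Neither document gives an SD, a correlation between prior slope and Week 28 change, or a power figure for this endpoint.

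**The concern.** A patient's prior rate of decline should predict little of the change at Week 2 and much more of it at Week 28. A main effect forces the two coefficients to be equal. With unstructured covariance, generalised least squares gives most weight to the early visits, where the variance is small, so the common value sits near what Week 2 needs.

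Measurement error in the baseline score lowers it further. An upward error raises the computed prior slope and lowers every change score, which induces a negative association at all visits.

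At stake is the precision of the main continuous test of function. Treatment is randomised and treatment by visit is in the model, so the Week 28 contrast stays valid. No claim is made about the SVC model or about any supportive analysis in redacted text.

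**Working it through.** **The plan's own figure.** The only sample size stated is for the primary responder test (SAP 4.3): "on NurOwn® to be 35% and on Placebo to be 15"%, two-sided 0.05, 90% power.

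n = [1.96·√(2·0.25·0.75) + 1.2816·√(0.35·0.65 + 0.15·0.85)]² / 0.20² = (1.200 + 0.764)² / 0.04 = 96.4, so 97 per arm. It reproduces, and it does not depend on the MMRM.

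**Mechanism by hand.** Take ALSFRS-R visits at weeks −19, −15, −11, −7.5 and 0 (from the schedule). The mean is −10.5, the deviations are −8.5, −4.5, −0.5, 3 and 10.5, and the sum of squares is 212. One month is 30.4375/7 = 4.348 weeks.

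- A 1-point baseline error moves the prior slope by 10.5/212 × 4.348 = 0.215 points/month, and moves every change score by −1.
- The error variance of the prior slope is 4.348²/212 = 0.089 times the visit variance.

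Assume a between-patient slope SD of 0.5, a visit SD of 1.25 with independent errors, and a later slope equal to the prior slope plus an independent change. Leave out the entry rule and the other covariates. Then:

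- Var(prior slope) = 0.25 + 0.089 × 1.5625 = 0.389.
- Cov with change at t months = 0.25·t − 0.215 × 1.5625 = 0.25·t − 0.336.
- Coefficient needed at Week 2 (t = 0.46): (0.115 − 0.336)/0.389 = −0.57.
- Coefficient needed at Week 28 (t = 6.44): (1.610 − 0.336)/0.389 = 3.27.

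The two differ in sign. A common coefficient is b = Σ w_t·b_t, with weights w proportional to Σ⁻¹1, where Σ is the residual covariance matrix and 1 a vector of ones. The Week 28 SE relative to slope-by-visit is √[1 + (b₂₈ − b)²·Var(S)/σ²₂₈], where S is prior slope and σ²₂₈ the Week 28 residual variance under slope-by-visit. If b is near 0 this is 1/√(1 − R²), with R the correlation of prior slope with Week 28 change: 1.0% for R = 0.14, 2.1% for 0.20, 5.9% for 0.33, 9.1% for 0.40.

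**Full calculation.** Large-sample GLS on 400,000 simulated patients, with the entry rule applied: "Decline in ALSFRS-R total score of 3 or more points in the 12 weeks preceding randomization". Assumed grid (81 settings):

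- slope SD 0.4, 0.5 or 0.6 per month
- visit SD 1.0, 1.25 or 1.5
- mean prior slope −0.8, −1.0 or −1.2
- error correlation 0, 0.5 or 0.8 per month

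In each setting the SD of slope change was solved so that 15% of placebo patients improve by at least 1.25 points/month (median SD 0.91).

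| Quantity, unstructured covariance | Median | Range |
|---|---|---|
| Coefficient needed at Week 28 | 3.1 | 0.9 to 5.1 |
| Coefficient needed at Week 2 | – | −1.7 to 0.35 |
| Common coefficient as planned | −0.3 | −1.9 to 0.01 |
| SE, planned / slope omitted | 1.003 | 1.000–1.029 |
| SE, planned / slope-by-visit | 1.030 | 1.008–1.068 |

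The 10th–90th percentile of the last row is 1.014–1.059. Squared, that is 1.03–1.12, or 3–12% more patients. A contrast with 80% power under slope-by-visit keeps Φ(2.802/1.014 − 1.96) = 79% to Φ(2.802/1.059 − 1.96) = 75%.

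**Sensitivity.**

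- Calibrated to 10% placebo responders, the median loss is 4.5% (1.4–10.2%); to 20%, it is 2.0% (0.5–4.5%).
- A second grid let the correlation between prior and later slope vary. It kept the 175 settings matching both planning rates (12–18% responders, 10–20% halted). Median loss 4.9%, 10th–90th percentile 0.9–9.6%, maximum 14.5%.
- Fallback covariances (27 settings): planned/slope-by-visit 1.005–1.095 for TOEPH, ARH(1) and CSH; 1.001–1.016 for TOEP, AR(1) and CS.

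**Finite samples.**

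- N = 200, 20% dropout, 5% intermittent missing, 200 replicates in each of four settings: mean SE ratios 1.045, 1.028, 1.044 and 1.009; ratios of empirical SDs 1.043, 1.026, 1.060 and 1.013. The slope-by-visit SE was smaller in 753 of 800 replicates, and mean treatment estimates agreed within 0.03.
- A separate check with N = 190, complete data and 1,500 replicates gave model-SE losses of 1.1%, 3.4% and 5.0% (empirical 1.4%, 3.1%, 5.4%) in three settings, and 11.4% (empirical 10.3%) where prior and later slopes were strongly correlated.
- Its runs with 20% dropout (200 replicates) gave 1.1%, 3.4% and 4.8% on model SEs, but −1.6%, −0.2% and 4.7% on empirical SDs. That is too few replicates to settle differences this small.

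**The case against.** The strongest reply is that nothing here is wrong. A pre-specified main effect gives a valid test, no document contradicts another, and no stated figure changes. That stands: this is an efficiency point only.

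The reply also holds that the loss hardly touches a confirmatory decision, because the "primary efficacy endpoint and key secondary efficacy endpoints will be tested sequentially" and this test comes third. The full sequence was simulated with 100 per arm, a uniform slope shift, five settings and 10,000 trials each. At 35% versus 15%, the chance that all three tests succeed changes by at most 0.04 percentage points, even with a 6.8% SE loss. At half that effect the gate opens in only 19–24% of trials, and joint success changes by 0.07–0.30 points at a 3.0% loss and 0.33–0.61 at 6.8%. This stands too, and it limits the importance of the point.

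The size rests on assumed variances, and the two grids differ at the median (3.0% and 4.9%). The 15% is a planning value that already allows for discontinuation. The main grid was not fitted to the second planning rate, about 15% of placebo patients halted; in a rerun of it 7–16% were halted. Ceiling and integer scoring were ignored, missingness was completely at random, and the finite-sample fits were ML without Kenward–Roger. These points widen the uncertainty about size. They do not reverse the direction: the calculated SE was never smaller under the planned model, in any setting or covariance structure.

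Under TOEP, AR(1) and CS the planned main effect is neutral or helps (0.968–1.003 against omitting slope), and the gain from the interaction is small.

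**Conclusion.** The point holds as a modest loss of efficiency. Under the first-line covariance the slope covariate buys almost nothing at Week 28, and the SE is about 1–6% larger than with slope-by-visit. That range is the 10th–90th percentile over an assumed grid tied to 15% placebo responders. It is not a document figure, and its upper end is not a bound: stronger persistence of slope from before to after treatment gives more.

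Taken alone, without the gate, the test loses little at the planned effect. If 35% versus 15% arises from a uniform slope shift, both models have at least 98.9% power and differ by at most 0.6 points. At half that effect, median power is 62% as planned and 65% with slope-by-visit (gain 0.7–5.6 points). The practical return is mostly a tighter Week 28 estimate. There is no bias, no type I error problem, and no effect on the 97 per arm.

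**What to change.** In SAP 8.4, add the pre-treatment slope-by-visit interaction to the ALSFRS-R MMRM and take the Week 28 LS-mean difference from that model. Baseline score can stay a main effect, since adding baseline-by-visit as well changes the SE by only about 0.1%. The covariance list needs no change.

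The cost is one term in one model statement: 8 post-baseline visits, so 8 − 1 = 7 extra mean parameters, no new covariance parameters and no new data. The risk of non-convergence rises slightly, and the listed fallbacks cover it. In the weakest settings the gain is close to nil.

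Timing matters, because after unblinding the same change would look data-driven. SAP 2 already provides a route: additional changes "will be made prior to database lock and unblinding of the study data and captured in an appendix to the SAP".

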# 8. EFFICACY

## 8.1. General Considerations

Descriptive statistics for continuous and categorical variables will be presented as described in [Section 6.4](#).

Each statistical test will be performed at Type I error  $\alpha=0.05$  (Two-sided).

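### If the unstructured fit of the ALSFRS-R MMRM fails, most of the listed fallback structures can understate the Week 28 standard error when slopes differ between patients; a low-priority safeguard is to refit first and use a sandwich error

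*SAP*

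**What the plan says.** SAP 8.4 analyses the change in ALSFRS-R from baseline to Week 28 with an MMRM. Its terms are treatment, visit, their interaction, and five baseline covariates entered as main effects. The within-patient covariance is unstructured. The contingency reads: "If the unstructured covariance structure fails to converge following covariance structures will be tested in order below". The list is TOEPH, ARH(1), CSH, TOEP, AR(1), CS, and the selection rule is "The first covariance structure that converges will be used".

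On inference, the section says: "The Kenward-Roger approximation will be used to estimate denominator degrees of freedom for unbalanced data". It names no empirical (sandwich) standard error, no check of fit and no second attempt at the unstructured model before the list is entered.

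The test is confirmatory. SAP 8.1 states: "Each statistical test will be performed at Type I error" 0.05, two-sided. SAP 8.2 states: "The primary efficacy endpoint and key secondary efficacy endpoints will be tested sequentially to account for multiplicity and preserve overall Type I error". The SVC analysis in SAP 8.4 is defined by reference to this model, so it inherits the same rule.

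**The concern.** ALSFRS-R falls over time, and the trial's primary endpoint presumes that the rate differs between patients. When rates differ, the change from baseline fans out. Its variance grows with time, and so does the correlation between one visit and the next.

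TOEPH, ARH(1) and CSH let the variance differ by visit but not the neighbouring-visit correlation. TOEP, AR(1) and CS allow neither to change. The Toeplitz and autoregressive forms also treat visits as equally spaced, although Weeks 2 and 4 are two weeks apart and later visits four.

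Fitted by likelihood to a fanning-out covariance, such a structure can settle on a Week 28 variance that is too small. Kenward-Roger allows for having estimated the covariance parameters; it takes the structure itself as correct. The confidence interval would then be too narrow, and the 5% level on which the fixed sequence relies would not hold for this test.

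**Working it through.** **The plan's own figure.** The only sample-size calculation is for the responder endpoint: responders assumed "on NurOwn® to be 35% and on Placebo to be 15"%, and "Utilizing a Chi-square test with Type I error rate of 0.05 two-sided and 90% power we would require 97 participants per treatment arm". With p̄ = 0.25:

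n = [1.960·√(2·0.25·0.75) + 1.2816·√(0.35·0.65 + 0.15·0.85)]² / 0.20² = (1.2002 + 0.7636)² / 0.04 = 96.4, so 97 per arm.

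This reproduces. Power at 100 per arm is 91.0%. The SAP gives no SD, standard error or covariance for the MMRM, so the rest needs assumptions.

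**Inputs**
- From the SAP: "A sample size of approximately 100 participants per arm (approximately 200 participants total) will be randomized"; post-baseline visits at Weeks 2, 4, 8, 12, 16, 20, 24 and 28; the six structures and their order; two-sided 0.05.
- Assumed: SD of patient-specific slopes 0.5, 0.7 or 1.0 points/month; visit SD 1.0 or 1.5; complete data.

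**Method.** With t in months (weeks × 7 / 30.4375), the covariance of change from baseline is

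Σ = slopeSD²·t·t′ + visitSD²·(J + I),

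where J is the all-ones matrix and carries the shared baseline error. Each structure S was fitted at its large-sample limit by minimising log|S| + trace(S⁻¹Σ). With complete data and a separate mean for each arm and visit, the Week 28 estimate is the same under every structure; only its reported SE changes. So SE ratio = fitted SD / true SD at Week 28, and type I error = 2·[1 − Φ(1.96 × ratio)].

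**One setting in full** (slope SD 0.7, visit SD 1.5).
- Week 28: t = 6.44, variance 0.49 × 41.47 + 2 × 2.25 = 24.82, SD 4.98.
- Week 2: t = 0.46, variance 0.49 × 0.2116 + 4.5 = 4.60. The variance ratio is 5.4.
- True SE of the difference: 4.98 × √(2/100) = 0.705.
- TOEPH ratio 0.843, so its reported SE is 0.594 and the type I error is 2·[1 − Φ(1.652)] = 9.9%.

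**All six settings.** The Week 28 / Week 2 variance ratio is 3.3-19.7. The neighbouring-visit correlation rises from 0.51-0.57 (Weeks 2-4) to 0.83-0.97 (Weeks 24-28).

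| Structure | SE ratio | Type I error |
|---|---|---|
| TOEPH | 0.76-0.89 | 8.2-13.6% |
| ARH(1) | 0.79-0.89 | 8.1-12.2% |
| CSH | 0.96-0.97 | 5.7-6.1% |
| TOEP | 0.74-0.77 | 13.0-14.8% |
| AR(1) | 0.69-0.76 | 13.8-17.7% |
| CS | 0.62-0.74 | 14.5-22.3% |

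**Other assumed covariances**
- Wider random-slope grid (visit SD 0.7-2.0, with or without shared baseline error, dropout 0 or 25%): TOEPH 6.8-15.1%, ARH(1) 6.6-13.1%, CSH 5.5-7.2%, TOEP 11-19%, AR(1) 11-22%, CS 12-28%.
- Brownian drift without random slopes: TOEPH 8.2-9.3%, CSH 5.1-5.9%.
- True covariance ARH(1) or CSH with growing SD: TOEPH 5.0%, ARH(1) 4.5-5.0%, CSH 3.9-5.0%, but TOEP, AR(1) and CS 18-25%.

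**Simulation.** REML fits under the null, 100 per arm, with SAP-type covariates, missing-at-random dropout, integer scores and the entry criterion on prior decline; two scenarios of 748 and 544 trials.

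| Fit | Scenario 1 | Scenario 2 |
|---|---|---|
| Unstructured | 4.4% | 6.8% |
| TOEPH | 10.0% | 10.5% |
| ARH(1) | 9.4% | 10.5% |
| CSH | 4.7% | 7.2% |
| TOEP | 13.8% | 15.4% |
| AR(1) | 16.3% | 16.7% |
| CS | 20.7% | 17.8% |
| TOEPH with sandwich SE | 4.4% | 6.6% |

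The Monte Carlo error is about 0.8-1.3 points for TOEPH and unstructured. Pooled, TOEPH with the sandwich error gives (0.044 × 748 + 0.066 × 544) / 1,292 = 5.3%, and unstructured gives 5.4%. The unstructured fit converged in all 1,292 trials.

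**Limits.** A t reference with 190 df stood in for Kenward-Roger. Simulated responder rates were 4-5%, below the SAP's 15% for placebo, so simulated slope variability is on the low side. Only ALSFRS-R was examined, not SVC.

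**The case against.** The strongest objection is that the trigger is remote. Unstructured is the specified model, and it never failed in 1,292 simulated trials. By the rule of three, the failure probability in those scenarios is below 3/1,292 = 0.23%. Multiplied by the largest TOEPH excess in the main grid, 13.6 − 5 = 8.6 points, that adds at most about 0.02 points to the unconditional type I error. The test is also reached only after the primary and first key secondary endpoints succeed. SAP 6.8.1 further mentions multiple imputation for change-from-baseline analyses; if the MMRM is run on completed data, failure is less likely still. This stands and sets the priority. One caution: the simulated unstructured fits used a Cholesky parametrisation, so the count supports the refit proposed below more directly than it describes a default software run.

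The second objection is that an ordered, prespecified list prevents data-driven selection and puts the three heterogeneous structures first. That is also right, and the fix keeps a fixed order. But the list does not protect the error rate once used: CSH, the near-nominal structure, is reached only if TOEPH and ARH(1) both fail.

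A reader might infer that every fallback is invalid, or that 8-14% is a property of TOEPH. The documents support neither. They give no covariance; CSH is close to nominal throughout; and TOEPH and ARH(1) hold their level if the true covariance lies in their families. Nor is it true that none of the six lets the variance grow, since three do.

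**Conclusion.** The point holds as a conditional one. If the unstructured model fails and patients differ in their rate of decline, the fallback rule would test the Week 28 difference at about 8-14% under TOEPH, 8-12% under ARH(1), about 6% under CSH, and 13-22% under TOEP, AR(1) or CS, instead of 5%. These figures rest on the assumed slope and visit SDs. TOEP, AR(1) and CS gave too small a standard error under every covariance tried.

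The documents make between-patient slope variation plausible but do not measure it. A 15% placebo responder rate at 1.25 points/month with no mean change implies an SD of slope change of 1.25 / 1.036 = 1.2 points/month, but that figure mixes pre- and post-treatment slopes with measurement error.

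A reader might infer that the confirmatory ALSFRS-R analysis is itself unsound. It is not: the unstructured model is appropriate and very likely to be the one reported. This is a low-priority safeguard for a confirmatory test, worth having because a different fallback chosen after unblinding would be data-driven.

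**What to change.** In SAP 8.4, replace the fallback rule with three steps:

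1. Refit the same unstructured model in Cholesky form, FA0(8) for the eight post-baseline visits, or with other starting values.
2. If that fails, use a fixed order of heterogeneous structures (for example TOEPH, ARH(1), CSH), take the first that converges, and report the empirical (sandwich) standard error with between-within degrees of freedom for the treatment difference.
3. Drop TOEP, AR(1) and CS, or keep them only as a last resort with the sandwich error.

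State whether the same steps apply to the SVC model, which inherits the rule.

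The cost is a few lines of text and an option in the model call. The SAP's introduction allows such changes before database lock and unblinding. The downside is that Kenward-Roger is not used in the fallback, which is immaterial at about 200 participants. The sandwich error corrects the variance only: with dropout, a wrong working covariance can still bias the Week 28 estimate, which is why the unstructured refit comes first.
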